8.1 Definitions

Unanticipated Adverse Device Effect (UADE)

A UADE is any serious adverse effect on health or safety or any life-threatening problem or death caused by, or associated with, a device if that effect, problem or death was not previously identified in nature, severity, or degree of incidence in the investigational plan or IDE application (including a supplementary plan or application), or any other unanticipated serious problem associated with a device that relates to the rights, safety, or welfare of subjects.

Adverse Effect (Event)

Any untoward medical occurrence in a subject involved in clinical study of an investigational device; regardless of the causal relationship of the problem with the device or, if applicable, other study related treatment(s).

General Physical Examination Findings

At screening, any clinically significant abnormality should be recorded as a preexisting condition. At the end of the study, any new clinically significant findings/abnormalities that meet the definition of an adverse event must also be recorded and documented as an adverse event.

Hospitalization, Prolonged Hospitalization or Surgery

Any adverse event that results in hospitalization or prolonged hospitalization should be documented and reported as an unanticipated adverse device effect unless specifically instructed otherwise in this protocol. Any condition responsible for surgery should be documented as an adverse event if the condition meets the criteria for an adverse event.

Neither the condition, hospitalization, prolonged hospitalization, nor surgery are reported as an adverse event in the following circumstances:

- Hospitalization or prolonged hospitalization for diagnostic or elective surgical procedures for a preexisting condition. Surgery should **not** be reported as an outcome of an adverse event if the purpose of the surgery was elective or diagnostic and the outcome was uneventful.
- Hospitalization or prolonged hospitalization required to allow efficacy measurement for the study.
- Hospitalization or prolonged hospitalization for therapy of the target disease of the study, unless it is a worsening or increase in frequency of hospital admissions as judged by the clinical investigator.

Post-study Adverse Event

All unresolved adverse events should be followed by the investigator until the events are resolved, the subject is lost to follow-up, or the adverse event is otherwise explained. At the last scheduled visit, the local investigator should instruct each subject to report, to the local investigator, any subsequent event(s) that the subject, or the subject's personal physician, believes might reasonably be related to participation in this study. The local investigator should notify the study regulatory sponsor of any death or adverse event occurring at any time after a subject has discontinued or terminated study participation that may reasonably be related to this study. The sponsor should also be notified if the local investigator should become aware of the development of problems, cancer or of a congenital anomaly in a subsequently conceived offspring of a subject that has participated in this study.

Preexisting Condition

A preexisting condition is one that is present at the start of the study. A preexisting condition should be recorded as an adverse event if the frequency, intensity, or the character of the condition worsens during the study period.

Unanticipated Problems Involving Risk to Subjects or Others (UPIRTSO)

Any unanticipated problem or adverse event that meets all of the following three criteria:

- Serious: Serious problems or events that results in significant harm, (which may be physical, psychological, financial, social, economic, or legal) or increased risk for the subject or others (including individuals who are not research subjects). These include: (1) death; (2) life threatening adverse experience; (3) hospitalization - inpatient, new, or prolonged; (4) disability/incapacity - persistent or significant; (5) birth defect/anomaly; (6) breach of confidentiality and (7) other problems, events, or new information (i.e. publications, DSMB reports, interim findings, product labeling change) that in the opinion of the local investigator may adversely affect the rights, safety, or welfare of the subjects or others, or substantially compromise the research data, **AND**
- Unanticipated: (i.e. unexpected) problems or events are those that are not already described as potential risks in the protocol, consent document, not listed in the Investigator's Brochure, or not part of an underlying disease. A problem or event is "unanticipated" when it was unforeseeable at the time of its occurrence. A problem or event is "unanticipated" when it occurs at an increased frequency or at an increased severity than expected, **AND**

- Related: A problem or event is "related" if it is possibly related to the research procedures.

Adverse Event Reporting Period

For this study, the study treatment follow-up period is defined from enrollment in the study to 6 months after balloon removal (12 months from balloon insertion). Adverse events will be captured and reported from enrollment to the end of the study treatment follow-up.

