- Continuing nausea and vomiting or possibly the prevention of vomiting
- A feeling of heaviness in the abdomen
- Abdominal or back pain, either steady or cyclic
- Gastroesophageal reflux
- Influence on digestion of food
- Blockage of food entering into the stomach
- Bacterial growth in the fluid which fills the balloon which could cause infection, fever, cramps, and diarrhea
- Injury to the lining of the digestive tract as a result of direct contact with the balloon, grasping forceps, or as a result of increased acid production by the stomach which could lead to ulcer formation and possible surgical correction
- Death due to complications related to gastric or esophageal perforation
- Balloon deflation and subsequent replacement
- Acute pancreatitis
- Spontaneous over inflation

Possible risks which may occur from the subject's endoscopy procedure include difficulty swallowing, injury to the lining of the esophagus or stomach, perforation (a hole in the wall of your stomach or esophagus), bleeding, infection, inflammation, dental injury, pain following the procedure with the potential for hospitalization to control pain, post procedure fluid collection with or without abscess or death.

The risk of monitored controlled sedations medications used to make the subject drowsy can cause breathing difficulties or a drop in blood pressure. These side effects are easily observed and managed by the anaesthesia team. These medications may cause some inflammation at the intravenous site where the drugs are given again that will be discussed and explained by the anaesthesia team prior to the procedure.

If any gastric ulceration were identified at the time IGB removal after 6 months, subjects will be treated with proton pump inhibitors therapy with dose and duration of therapy determined by the study PI. These subjects will be followed clinically until complete resolution.

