3.4 Primary Safety Endpoints

- Incidence of all serious adverse events including unanticipated adverse effects (balloon migration, small bowel obstruction, luminal GI perforation, ulcer formation, liver abscess formation, bleeding, biliary obstruction or injury, aspiration, infection, abdominal pain requiring hospitalization, nausea and dehydration requiring intravenous fluids, and death). All adverse events will be captured and graded for severity using Common Terminology Criteria for Adverse Events (CTCAE) scale. [27]
- Early balloon intolerance requiring removal.
- Balloon deflation rates (see Orbera PMA)

4 Subject Selection, Enrollment and Withdrawal

Adolescents age 14-17 who are seen at Mayo Clinic-Rochester in community pediatrics, pediatric GI, pediatric endocrinology, or the pediatric weight management clinic, or at Mayo Clinic Health System (MCHS) with a $BMI > 35 \text{ kg/m}^2$ with one severe comorbidity or $BMI > 40 \text{ kg/m}^2$ with two or more mild comorbidities as per the ESPAGHAN guidelines for

bariatric intervention in children with severe obesity. [14] Recent meta-analysis supported the safety and benefit of IGB use in higher BMI (range 35-55).[24] Subjects that meet these criteria can be referred to the PI, co-investigators, or study coordinator to approach for possible participation in this research study.

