This is a pilot study of 12 subjects only, so results will be largely descriptive. Standard statistical analysis will be performed. We will use t-tests or alternative measures will be used to test whether weight loss was significant from baseline to each of the follow up points.

8 Safety and Adverse Events

All adverse events occurring during the study, including those not meeting the criteria of an Unanticipated Adverse Device Effect (UADE) will be recorded on the appropriate case report form. Records of these events will be maintained and reports submitted to the FDA and IRB according to the regulatory requirements. All adverse events will be reported. Expected clinical adverse events and anticipated adverse device effects are those listed in Section 1.5.2.

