8.5 Stopping Rules

- 1 death
- 1 severe anticipated adverse event, including but not limited to:
 - Esophageal or gastric perforations
 - Peptic ulcer related bleeding requiring transfusion
 - Balloon deflation resulting in small bowel obstruction
 - Severe dehydration
 - Persistent vomiting and retching causing esophageal perforation requiring hospitalization
- 1 severe unanticipated adverse event, including but not limited to:
 - Any complication required more than 3 days of hospitalization
 - Any surgical intervention
 - Any admission to the Intensive Care Unit

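### Section 8.1 makes unanticipated adverse device effect (UADE) the default label for a hospitalised adverse event, against its own UADE definition, so UADE counts and expedited UADE reports may be inflated

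*Combined protocol and SAP*

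**What the plan says.** All references are to the combined protocol and SAP.

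- **Section 8.1, UADE definition.** The effect must be serious, must be "caused by, or associated with, a device", and must not already be identified in nature, severity or degree of incidence in the investigational plan or IDE application. A second limb covers other unanticipated serious problems associated with a device.
- **Section 8.1, adverse event definition.** No causal link to the device is needed.
- **Section 8.1, hospitalisation paragraph.** "Any adverse event that results in hospitalization or prolonged hospitalization should be documented and reported as an unanticipated adverse device effect", with the qualifier "unless specifically instructed otherwise in this protocol". Three exclusions follow, introduced by "Neither the condition, hospitalization, prolonged hospitalization, nor surgery are reported as an adverse event in the following circumstances": diagnostic or elective procedures for a preexisting condition, admission to allow efficacy measurement, and therapy of the target disease unless it has worsened.
- **Section 8, opening paragraph.** "Expected clinical adverse events and anticipated adverse device effects are those listed in Section 1.5.2".
- **Section 1.5.2.** The endoscopy risks include "pain following the procedure with the potential for hospitalization to control pain".
- **Section 8.5.** The anticipated limb includes an event that requires hospitalisation (persistent vomiting and retching with oesophageal perforation). The other limb is "1 severe unanticipated adverse event, including but not limited to" a short list of examples.
- **Sections 8.3 and 8.3.2.** A UADE is reported to the IRB within 5 working days and to the FDA within 10, on Form 3500A.
- **Section 3.4.** The primary safety endpoint begins "Incidence of all serious adverse events including unanticipated adverse effects (balloon migration, small bowel obstruction, luminal GI perforation" and continues with further events, among them abdominal pain that leads to admission.

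**The concern.** Hospitalisation is a mark of seriousness. The hospitalisation paragraph treats it as if it also established that the event was linked to the device and was unforeseen. Two kinds of event then receive a label they do not meet by definition: an admission unrelated to the balloon, and an admission for something the protocol already lists as expected.

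At stake are the number of UADEs and the expedited reports that follow from the label. In a 12-subject pilot of a device new to this age group, a single mislabelled admission would stand out in any account of unexpected device effects.

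**Working it through.** The documents state no UADE rate or admission rate, so there is no planned figure to reproduce. The main check is a comparison of texts.

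**1. What each passage requires for the UADE label**

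| Passage | Serious? | Device-associated? | Unanticipated? |
|---|---|---|---|
| 8.1 UADE definition | required | required | required |
| 8.1 hospitalisation paragraph | implied by admission | not tested | not tested |
| 8.1 UPIRTSO definition, for comparison | required; admission is one way to meet it | required separately | required separately |

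The UPIRTSO text shows the usual structure: admission satisfies seriousness only.

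**2. Events on which the two 8.1 rules disagree**

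- *Admission for post-procedure pain.* It is listed in 1.5.2, so under Section 8 it is anticipated. Unless it exceeds what the plan identifies in severity or incidence, the definition says it is not a UADE. The hospitalisation paragraph says it is.
- *Admission with no link to the balloon.* It is an adverse event, because causality is not needed for that term. The definition says it is not a UADE; the hospitalisation paragraph says it is.
- *The hospitalised event in the anticipated limb of 8.5.* The stopping rule calls it anticipated; the default in 8.1 calls it unanticipated.

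**3. Whether the escape clause or the exclusions remove the conflict**

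The clause needs a specific contrary instruction. None of the three exclusions covers an anticipated or an unrelated admission. The pointer to 1.5.2 says which events are expected but does not say how to report them when they lead to admission.

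**4. What depends on the label**

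| Item | Changes with the UADE label? |
|---|---|
| UADE count | yes |
| UADE reports to IRB (5 working days) and FDA (10 working days, Form 3500A) | yes |
| Section 3.4 incidence of all serious adverse events | no; the event counts under either label |
| Section 8.5 stopping rule | not shown; it does not use the term, and one severe event suffices in either limb |
| DSMB authority to suspend (8.6.1) | no; any serious event requiring hospitalisation qualifies |

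**5. Size**

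One mislabelled subject among 12: 1/12 = 8.3%, against 0/12.

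For scale only, let p be an assumed per-subject probability of admission for an adverse event. With 12 independent subjects, the chance of at least one admitted subject is 1 − (1 − p)^12.

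| Assumed p | Calculation | Chance of at least one | Expected subjects, 12p |
|---|---|---|---|
| 1% | 1 − 0.99^12 | 11% | 0.12 |
| 2% | 1 − 0.98^12 | 22% | 0.24 |
| 5% | 1 − 0.95^12 | 46% | 0.60 |
| 10% | 1 − 0.90^12 | 72% | 1.20 |

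These are upper bounds on the chance of a false UADE, because some admissions would be true UADEs and some would fall under the exclusions.

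**The case against.** The strongest reply is that later steps would catch the error. Under 8.2 each event is assessed for seriousness and causality. Under 8.3 the sponsor-investigator evaluates the event and decides what reporting is needed, and Form 3500A under 8.3.2 is for effects determined to be UADEs. The UADE definition, with the pointer to 1.5.2, might itself be read as the contrary instruction that the escape clause allows for. Any error is also towards over-reporting, and no event is lost. This has force: it is why the count may be inflated rather than must be. It does not remove the defect, because staff are left with two conflicting rules in one section and nothing that says which prevails.

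A reader might infer three stronger things that the documents do not support.

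- *That every hospitalised event becomes a UADE.* The escape clause and the three exclusions rule that out.
- *That the stopping rule would be triggered falsely.* Section 8.5 is not keyed to UADE status, and its hospitalisation example in the unanticipated limb is a stay of more than 3 days. A false trigger would need a non-severe or unrelated short admission to be read into that open-ended limb, and nothing in the text requires this.
- *That the primary safety endpoint would be wrong.* It counts all serious adverse events, and the statistical plan in Section 7 contains no separate UADE analysis.

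The bracket in 3.4 is ambiguous rather than wrong. It can attach to all serious adverse events or only to the unanticipated ones. On the second reading it clashes with 1.5.2, which already describes migration, obstruction and perforation as known risks.

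**Conclusion.** The contradiction within Section 8.1 is real and can be seen from the text alone. Its reach is limited to the UADE label: the UADE count and the IRB and FDA reports tied to it may be inflated by anticipated or unrelated admissions. One such case is worth 8.3 percentage points in a trial of 12. How likely that is cannot be derived from the documents; the 11% to 72% range rests on assumed admission rates of 1% to 10%, on independent subjects, and on literal use of the default. The IDE application, which the UADE definition also invokes, is not among the documents, so the full set of previously identified effects cannot be checked here. The point deserves correction because a stated rule, followed as written, gives labels that the protocol's own definition rejects.

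**What to change.** Amend Section 8.1 in three respects.

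1. In the hospitalisation paragraph, have an adverse event that results in admission documented and reported as a serious adverse event, keeping the three exclusions.
2. Add a short definition of serious adverse event. Section 8.1 has none; seriousness is described only within the UPIRTSO text, although the primary safety endpoint relies on the term.
3. State that a serious adverse event is classified as a UADE only if it also meets the 8.1 definition: associated with the device, and not previously identified in nature, severity or degree of incidence in the investigational plan (including 1.5.2) or the IDE application. A check against the 1.5.2 list alone would not be enough, since a listed event can still qualify through greater severity or frequency.

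Optionally, say in 3.4 that the bracketed list gives serious adverse events of interest and is not a list of unanticipated effects.

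The cost is a short wording amendment. It needs no added data, visits or procedures, and it changes no clinical rule.

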4.4.2 Data Collection and Follow-up for Withdrawn Subjects

If a patient is withdrawn from the study for reasons other than severe adverse events, the IGB will be removed from the patient at a time that works for the patient and within 6 months of insertion. The patient will be followed as per the standard clinical protocol for the IGB to ensure safety. Weight and safety data will be collected until the IGB is removed. After IGB removal subjected will be followed clinically as per our protocol for additional six months to ensure safety.

5 Study Device

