6.6 Management of Device Failure

If there is a device malfunction during the initial endoscopic placement (e.g. balloon is deflated, perforated, or other failure), then the balloon will be replaced with a new balloon during the same procedure.

During the follow-up visits or phone calls, if there is concern that the balloon is malfunctioning or may be deflated after successful placement, which can be suggested by the lack of satiety, ability to eat larger meals, or failure to lose weight during two consecutive follow-up visits, an abdominal ultrasound assessment will be performed.

- If the balloon is intact, then no endoscopic assessment will be indicated.
- If there is evidence of balloon malfunction without complication, a new balloon will be placed.
- If the balloon is deflated in the stomach, it will be replaced endoscopically with a new balloon.
- If the balloon is not in the stomach and subject has no symptoms of small bowel obstruction, the subject will be observed for 3 days for spontaneous passage of the balloon. Serial abdominal x-rays will be performed to monitor progression of the balloon in addition to clinical follow-up of signs and symptoms that may indicate a small bowel obstruction (e.g. pain, bilious vomiting, etc.) If the balloon doesn't pass, an attempt to remove it endoscopically will be performed. If not reachable by the endoscopy, the subject will be referred for surgical removal.

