6.7 Removal of Balloon after 6 months by PI or Co-PI

The balloon will remain in the stomach if tolerated for 6 months, and then it will be removed endoscopically by a gastroenterologist ([name] or [name]). In order to prepare for the IGB removal, the subject will need to be on a liquid diet for 48 hours prior to its removal, and consume nothing by mouth for at least 12 hours prior to the IGB removal.

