6.8 Schedule of Events

Table 2 provides a complete list of tests, procedures, and questions which will take place at each study visit, along with a time period and range for each study visit.

Table 2: Schedule of Events

Visit Type	Screening Visit	-4 weeks (+4 weeks)	-2 weeks (+2 weeks)	Day 0	Visit 0	4 days (± 1 day)	Visit 1	2 weeks (± 1 week)	Visit 2	1 month (± 1 week)	Visit 3	2 months (± 1 week)	Visit 4	3 months (± 1 week)	Visit 5	4 months (± 1 week)	Visit 6	5 months (± 1 week)	Visit 7	6 months (± 1 week)	Visit 8	7 months (± 1 week)	Visit 9	8 months (± 1 week)	Visit 10	9 months (± 1 week)	Visit 11	10 months (± 1 week)	Visit 12	11 months (± 1 week)	Visit 13	12 months (± 1 week)	Visit 14
Inclusion & Exclusion Criteria	x																																
Consent	x																																
Psychological exam		x													x					x									x				
Blood sample: GI hormones (2)		x												x				x		x					x			x			x		
Stool sample (3)		x												x																			
Urine pregnancy test (females) (4)				x																													
EGD/IGB insertion (1,4)				x																													
EGD/IGB removal (1,5)																			x														
Other Blood & Urine samples (6)		x												x				x		x					x			x			x		
PN Q (7)	x																														x		
CES-D & SCAS (7)	x													x																	x		
WMC		x												x				x		x					x			x			x		
PE (8)		x	x			x	x	x	x		x		x		x		x	x	x	x	x	x	x	x		x	x	x	x				
GI nurse telephone questionnaire					x	x	x	x	x	x	x	x	x	x	x	x	x	x	x	x	x	x	x	x	x	x	x	x	x				

Key:

EGD: upper endoscopy

IGB: Intragastric Balloon

PN Q: Pediatric Nutrition Questionnaire

CES-D: Self-Report Depression Scale Questionnaire

SCAS: Spence Child Anxiety Scale Questionnaire

WMC: Weight Management Clinic visit with dietitian

PE: Physical Exam by pediatric endocrinologist or pediatric gastroenterologist

Footnotes:

1-The IGB will be provided at no cost by the manufacturer.

2-GI hormones include: Total Ghrelin; PYY; GLP-1; and Leptin.

3-A stool sample will be collected for a fecal antigen study for H. pylori (sensitivity > 96.8%) to exclude the presence of H. pylori prior to the initial endoscopic assessment.

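### Sections 8.1 and 4.4.2 give conflicting ends for adverse-event capture, so a withdrawn subject's safety window could close at balloon removal, six months later, or at month 12

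*Combined protocol and SAP*

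**What the plan says.** Section 8.1 (Adverse Event Reporting Period) sets one period for the study: "the study treatment follow-up period is defined from enrollment in the study to 6 months after balloon removal (12 months from balloon insertion". It then ties capture to that period: "Adverse events will be captured and reported from enrollment to the end of the study treatment follow-up".

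Section 4.4.2 covers withdrawn subjects. Its opening sentence concerns when the device comes out: "If a patient is withdrawn from the study for reasons other than severe adverse events, the IGB will be removed" at a convenient time within six months of insertion. A later sentence has weight and safety data collected up to removal and no further. The last sentence reads: "After IGB removal subjected will be followed clinically as per our protocol for additional six months to ensure safety".

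The planned dwell is conditional. Section 6.7 states: "The balloon will remain in the stomach if tolerated for 6 months". Table 2 in Section 6.8 places the removal visit at "6 months (± 1 week") and shows a single track of visits and calls ending at month 12.

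Earlier removal is expected in some subjects. Section 3.4 lists "Early balloon intolerance requiring removal" among the primary safety endpoints, and Sections 6.2 and 6.4 give further reasons for removal. Section 6.6 also provides for replacement: "If the balloon is deflated in the stomach, it will be replaced endoscopically with a new balloon". It does not say when the new balloon comes out, or which insertion date then counts.

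**The concern.** Section 8.1 treats two dates as one, although they coincide only on the planned schedule. Section 4.4.2 then gives withdrawn subjects a shorter period of study data collection, followed by clinical follow-up that is not said to feed the adverse-event record.

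A coordinator following Section 4.4.2 literally would stop recording at removal. One following Section 8.1 would continue for six more months, or to month 12. The incidence of all serious adverse events is a primary safety endpoint, and Section 8.1 defines adverse events regardless of cause. Events after removal would therefore count or not count depending on which sentence was followed, and subjects would be observed for different lengths of time without the report showing it. In a sample of 12, one subject handled differently changes an incidence by 1/12 = 8.3 percentage points.

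**Working it through.** **Inputs.** Planned dwell of 6 months (Section 6.7) with a window of one week either side (Table 2); the two end dates in Section 8.1; the end of data collection for withdrawn subjects in Section 4.4.2; 12 subjects (Section 7). Months are counted from first insertion, and *r* is the month of removal.

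**Formulas.**
- End A (Section 8.1, main clause) = r + 6
- End B (Section 8.1, bracket) = 12
- End C (Section 4.4.2, withdrawn subjects) = r
- B − A = 6 − r; A − C = 6; B − C = 12 − r

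**The plan's own equality.** At r = 6, A = 6 + 6 = 12 = B, so it reproduces on schedule. With removal a week early or late, A and B differ by one week, which has no practical weight.

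**Early removal.**

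| Removal (r) | C (withdrawn only) | A | B | B − A |
|---|---|---|---|---|
| 0.5 (week 2) | 0.5 | 6.5 | 12 | 5.5 |
| 1 | 1 | 7 | 12 | 5 |
| 3 | 3 | 9 | 12 | 3 |
| 5 | 5 | 11 | 12 | 1 |
| 6 | 6 | 12 | 12 | 0 |

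At week 2, A and B are 5.5 months apart, or 5.5/12 = 46% of the 12-month period. C and B are 12 − 0.5 = 11.5 months apart.

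**Replacement at month m.** The documents do not say whether the six months restart, so both cases are shown.
- *Dwell restarts (assumption).* Removal is at m + 6, A = m + 12, and End B leaves 12 − (m + 6) = 6 − m months of capture after removal. For m = 1, 3 and 5, that is 5, 3 and 1 months, with A at months 13, 15 and 17.
- *Removal at the original month 6.* A = B = 12 counted from first insertion, so nothing is lost. If insertion meant the new balloon, B would be m + 12, or months 13 to 17 for m = 1 to 5.

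**What other sections cover.** Under Section 5.4 all subjects are followed after removal according to Table 2, and Section 8.2 has adverse events solicited at every visit or contact. A subject with early removal who stays in the study is therefore questioned to month 12. After the study period, Section 8.2 still requires serious events that are at least possibly related to be recorded. Section 8.1 has deaths and adverse events that may reasonably be related notified to the sponsor, even after a subject has discontinued. Neither provision extends general capture to unrelated events.

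**The case against.** The strongest reply is that this is a drafting ambiguity with little consequence. Early removal is not withdrawal, and subjects who remain are seen and called to month 12. The main clause of Section 8.1 gives everyone six months off the device. Unresolved events are followed to resolution, related late events are reportable, and the analysis is descriptive with no comparator. The six months of clinical follow-up in Section 4.4.2 might also be meant to feed the adverse-event log.

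Much of this stands, and it confines the problem mainly to withdrawn subjects. It does not remove the conflict. Section 4.4.2 ends safety data collection at removal and calls what follows clinical follow-up, without saying that those observations enter the study record. The late-event provisions depend on a judgement of relatedness, whereas the endpoint does not.

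Three stronger readings are tempting, and the documents do not support them.
- *Subjects withdrawn for a severe event have no adverse-event window.* Section 8.1 defines the period for the study and exempts nobody. The limiting phrase in Section 4.4.2 belongs to its own sentence, on removal timing.
- *Events are understated in the subjects who fared worst.* This is not shown. The event that prompts removal is already captured, and two of the three primary safety endpoints (early intolerance and deflation) cannot newly arise once the balloon is out.
- *A replacement balloon shortens the window.* This follows only if the new balloon stays past the original month 6 and the bracket overrides the main clause. Neither is stated.

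**Conclusion.** The conflict is real and should be corrected. The two dates in Section 8.1 differ by 6 − r months, and Section 4.4.2 supplies a third, earlier end for withdrawn subjects. For withdrawal with removal at week 2, the possible ends are months 0.5, 6.5 and 12. That case is an illustration within what the plan allows, not a forecast.

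The practical exposure is limited to new events after removal in withdrawn subjects, chiefly those judged unrelated or never reported. Any balloon that stays in past month 6 adds to it: End B would then leave less than six months of capture after removal. For replacements, the figures of 5, 3 and 1 months rest on an assumed restart of the dwell. How many subjects will be affected is unknown, and no direction or size of bias can be claimed. The point concerns which events are eligible to be counted, and it is certain only as to the wording.

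**What to change.** 1. **Section 8.1.** Give one end date. For every subject in whom insertion was attempted, whatever the reason for removal or withdrawal and subject to continued consent, capture runs from enrolment to the later of (a) 12 months after first insertion and (b) 6 months after removal of the last balloon.
2. **Section 4.4.2.** Replace the sentence that stops weight and safety data at removal with a separate sentence applying the Section 8.1 adverse-event window to all withdrawals, and restate there how long weight is collected. Leave the clause on removal timing untouched, because deleting its exception would alter a clinical rule.
3. **Sections 6.6, 6.8 and 8.1.** Reconcile these on which insertion date applies after a replacement. The dwell time is for the sponsor to state; none is proposed here.

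**Cost.** After early removal the later date is month 12, so the visits and calls already in Table 2 suffice, although withdrawn subjects would need a few telephone contacts that they might not otherwise receive. If a balloon comes out after month 6, follow-up passes month 12. In the restarted-dwell illustration with replacement at month 5 it reaches month 17, which is 5 extra months, or about 17 × 52/12 = 74 weeks from insertion. The Study Summary gives 12 months of participation and 60 to 64 weeks overall, and the nurse calls end at month 11. Those entries, and the consent wording where it states duration, would then need to match.
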